## DOCUMENTATION, EVALUATION AND NOTIFICATION OF SAEs

All incidents will be captured as a part of this clinical study. At each contact with the patient, the investigator must seek information on adverse device effects by specific questioning and, as appropriate, by examination. Information on all adverse device effects should be recorded immediately in the source document, and also in the appropriate adverse effect case report form (CRF). All clearly related signs, symptoms, and abnormal diagnostic procedures results should be recorded in the source document.

In conformity with MDD Directive 93/42/EEC (Article 10), any incident resulting from a malfunction or deterioration in the characteristics and/or performance of the device or inadequacies in the

labeling that might lead or might have led to the death of a patient or user or to a serious deterioration in the state of health of the patient or user or any device deficiency that leads to a systematic recall will be reported to the appropriate authorities. During site visits, the Monitor will follow-up with the Investigator(s) to ensure they have transmitted the information to the appropriate authorities and that the appropriate documentation is retained onsite in the study regulatory binder.

The Investigator shall report all serious adverse events (anticipated or unanticipated) to the Sponsor's UK Legal Representative within 24 hours upon becoming aware of events.

All adverse device effects occurring during the study period must be recorded using the Adverse Event Source Documents and Case Report Forms provided by the Sponsor for documenting adverse events. The clinical course of each event should be followed until resolution, stabilisation, or until it has been determined that the study treatment or participation is not the cause. Serious adverse device effects that are still ongoing at the end of the study period must be followed up to determine the final outcome. Any serious adverse device effects that occur after the study period should be recorded and reported promptly to the appropriate authorities. A follow-up written report, documented on the Adverse Event CRF and including any related clinical documentation, shall be provided as soon as possible and shall include the following information, as applicable:

1. Patient Study ID
2. Event description
3. Statement as to whether it is considered anticipated or unanticipated
4. Statement as to the degree to which it is considered device-related, and why
5. Results of any diagnostic tests that were performed
6. Description of any medical intervention required
7. Status following the intervention
8. Investigator's signature and date on the AE CRF

The Investigator will continue to clinically monitor the adverse event per standard of care until it is resolved, stabilised, or the patient's status returns to pre-event status, documenting the status on appropriate CRFs, including any sequela.

The Sponsor will ensure compliance with all country-specific reporting requirements to the appropriate Ethical Committee and Competent Authority.

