## RETROSPECTIVE COLLECTION OF DATA

Protocol Version 00k extends the patient follow-up with visits at 48 and 60 months. The Protocol Version 00j had introduced additional follow-up visits at 18, 30 and 36 months. These protocols allow retrospective collection of data on any scheduled or unscheduled visit that the subjects participated in for the TRACER trial (if subject came back to the hospitals) before Versions 00j or 00k are approved by Ethic Committee (EC) and Competent Authority (CA).

Once Protocol Version 00k has been approved by relevant EC and CA, patients will be contacted and asked to consent to the additional visits and have their data collected. Patients who exited from the trial at 36 months as scheduled per protocol Version 00j will be contacted and requested to continue their follow-up up to 60 months as scheduled by Protocol Version 00k.

Two different versions of information letters will be sent depending on patient status (already exited or not). Each patient will have to sign this letter to approve collection of additional data.

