## SEVERITY AND CAUSALITY ASSESSMENT

The occurrence of Adverse Events (AE's) will be monitored during this study. All AE's will be recorded on the Adverse Event Form at onset and at each follow-up visit until resolved. To meet the objectives of this study, the following definitions will apply. (Definitions reference ISO 14155:2012-01 and MEDDEV 2.7/3, December 2010)

**Adverse Event (AE):** Any untoward medical occurrence, unintended disease or injury or any untoward clinical signs (including an abnormal laboratory finding) in patients, users or other persons whether or not related to the investigational medical device. This includes events related to the device or events related to the procedures involved (any procedure in the clinical investigation plan). For users or other persons, this definition is restricted to events related to investigational medical devices.

**Adverse Device Effect:** An adverse event related to the use of an investigational medical device, including adverse events resulting from insufficient or inadequate Instructions for Use, deployment, implantation, installation or operation, or any malfunction of the medical device or any event resulting from use error or intentional misuse of the medical device.

All AEs will be monitored from the time of the Harpoon Medical procedure through the 60 month follow-up visit. All AEs observed by the Investigator or staff during a physical or laboratory examination, interventional procedure, or mentioned by the patient either spontaneously or upon questioning will be recorded on the AE case report form. Information pertaining to all AEs will be reviewed and verified by the study Sponsor's Safety Team or its designated representative. The Investigator is responsible for assessing the severity of the AE, the causal relationship between any events and the clinical study procedure, activities or device. Additionally, the Investigator is responsible for providing appropriate treatment for the event and for adequately following the event until resolution. The following categories of adverse event severity are to be used:

- Mild: Awareness of a sign or symptom that does not interfere with the patient's usual activity or is transient, resolved without treatment and with no clinical sequela.
- Moderate: Interferes with the patient's usual activity

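### Sites are told to question patients about adverse device effects, but the safety endpoints count SAEs of any cause, so unrelated or outside-hospital SAEs may be under-ascertained; the event follow-up rules also conflict.

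*Combined protocol and SAP*

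**What the plan says.** All references are to the combined protocol and SAP.

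- **Endpoints.** Sections II and IV (Safety Goals) define safety as freedom from SAEs, with no relatedness condition. Section X tabulates freedom from SAEs through 36 months. It also gives the number and percentage of patients with one or more AEs or SAEs, with exact 95% limits, at each time point through 60 months.
- **Definitions.** Under Severity and Causality Assessment (section VIII), an adverse event counts "whether or not related to the investigational medical device". An adverse device effect is the subset related to use of the device.
- **Active questioning.** Under Documentation, Evaluation and Notification of SAEs, at each contact "the investigator must seek information on adverse device effects by specific questioning and, as appropriate, by examination". Two further sentences there, on source documents and case report forms, also speak of adverse device effects.
- **Recording.** Severity and Causality Assessment is broader. Events seen by staff or "mentioned by the patient either spontaneously or upon questioning will be recorded on the AE case report form", and AE monitoring runs from the procedure through 60 months.
- **Follow-up of an event.** There are three rules. Severity and Causality Assessment: "All AE's will be recorded on the Adverse Event Form at onset and at each follow-up visit until resolved". Documentation, Evaluation and Notification: until resolution, stabilisation, or "until it has been determined that the study treatment or participation is not the cause". Near the end of that same subsection: "until it is resolved, stabilised, or the patient's status returns to pre-event status".

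**The concern.** An endpoint that counts SAEs of any cause needs a question that is neutral as to cause. An instruction to ask about device effects presupposes the causality judgement that should come after capture. The study is single-arm and unblinded, and a stroke, bleed or heart-failure admission that patient and site regard as unrelated, or that another hospital treated, is the kind of event such a question can miss. Any loss raises SAE-freedom, so it favours the device.

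The follow-up conflict is a second and separate matter. Two sites could each follow a written rule and close the same event at different times, which makes outcome and resolution data inconsistent between them.

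**Working it through.** The plan gives no assumed SAE rate, safety sample size or margin, so there is no figure to reproduce. The check is a comparison of texts, followed by a scale for the possible effect.

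**1. Does broader text supply the missing question?**

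| Text | What it requires | What triggers it |
|---|---|---|
| Severity and Causality Assessment | All AEs recorded, related or not | Observed, or mentioned by the patient |
| Reporting Adverse Events | All SAEs on the CRF within 3 calendar days | Site awareness |
| Documentation, Evaluation and Notification | All SAEs reported within 24 hours | Becoming aware |
| Same subsection, opening sentence | Capture of all incidents | No method given |
| Same subsection, next sentence | Specific questioning | Each contact, but on adverse device effects |

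The first three rows govern what happens after the site knows of an event. Only the last says how the site is to find out, and it is the narrow one. No text requires a question about admissions elsewhere.

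**2. Do the follow-up rules agree?** No. The first and third have no causality exit; the second has one. The sentence with the exit follows one on adverse device effects, so it might be meant only for events first recorded as such. The conflict remains: an event later judged unrelated is still an AE, to be recorded at each visit until resolved.

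**3. Does the causality exit change the safety count?** Section X counts patients with at least one event. Follow-up can stop only on an event already recorded, and a patient with a recorded SAE stays in the numerator. What can be lost is outcome, resolution and later worsening.

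**4. Scale of a missed SAE.** Let x patients truly have an SAE among n, and let m of them have only SAEs that are missed. The recorded rate is (x − m)/n, so the shift is m/n.

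- n = 30 (the cohort in section X): 1/30 = 3.3 points per patient.
- n = 20 (the UK maximum): 1/20 = 5.0 points.
- n = 80 (section II maximum, 4 countries × 20): 1/80 = 1.25 points.

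The table shows patients with an SAE at n = 30, with exact limits: lower = Beta⁻¹(0.025; x, n − x + 1) and upper = Beta⁻¹(0.975; x + 1, n − x), where x is the recorded count. Where that count is zero, the lower limit is 0. Every true and missed count is an assumption.

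| True x | m = 0 | m = 1 | m = 2 | m = 3 |
|---|---|---|---|---|
| 3 | 10.0% (2.1–26.5) | 6.7% (0.8–22.1) | 3.3% (0.1–17.2) | 0.0% (0.0–11.6) |
| 6 | 20.0% (7.7–38.6) | 16.7% (5.6–34.7) | 13.3% (3.8–30.7) | 10.0% (2.1–26.5) |
| 9 | 30.0% (14.7–49.4) | 26.7% (12.3–45.9) | 23.3% (9.9–42.3) | 20.0% (7.7–38.6) |
| 12 | 40.0% (22.7–59.4) | 36.7% (19.9–56.1) | 33.3% (17.3–52.8) | 30.0% (14.7–49.4) |

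The intervals are wide beside a shift of one patient, but they describe sampling error only and make no allowance for missed events.

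**The case against.** The strongest reply is that the plan, read as a whole, already asks for everything. AEs are recorded whatever their cause. The SAE report form allows the answer no for both device and procedure relationship, so unrelated SAEs are expected. The schedule in section VIII lists medical history at follow-up visits and a release of medical information, and an interval history will usually bring out a stroke or an admission. The primary 30-day endpoint covers the procedure, the inpatient stay and one early visit, where misses are least likely.

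Much of this stands. It rules out the reading that sites may ask about device effects and nothing else, or that SAEs are in fact being under-counted: the documents contain no event counts. It does not close the gap. A medical history line does not say that admissions at any hospital must be asked about. In the copy reviewed the 60-month cell for it is blank, although that may be a table-reading fault and nothing here rests on it.

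Three other inferences are tempting and also fail:

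- **The retrospective-data subsection shuts out events treated elsewhere.** It permits use of data from past visits and does not bar a history taken later. It does not require one either.
- **Missed events at 48 and 60 months are kept from the Clinical Endpoint Committee.** Its adjudication ends at 36 months. Through 36 months a missed event cannot reach it; after that the analysis uses site reports in any case.
- **SAE-freedom at 60 months is inflated by some stated amount.** SAE-freedom is defined only to 36 months, and no rate of events or of misses is available.

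**Conclusion.** The concern holds as a mismatch of texts with a plausible one-sided risk. The mandatory question is narrower than the endpoint, and the broader duties begin only with awareness. The size is unknown; the scale is 3.3 points per missed patient at n = 30. This assumes that some SAEs come to light only if asked about, and that sites apply the questioning sentence as written. SAEs of any cause is meant subject to the plan's own exclusion of certain planned admissions and procedures. Section X describes the safety data as descriptive, so no test, power or margin changes.

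The three follow-up rules contradict one another and must be reconciled. A reader might infer that the causality exit lowers the SAE count. It does not remove a patient whose SAE is already recorded.

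**What to change.** 1. Under Documentation, Evaluation and Notification of SAEs, replace adverse device effects with all adverse events in the questioning sentence and the two recording sentences.
2. Add a causality-neutral prompt at each contact, including 60 months: any hospital admission, mitral intervention, stroke or bleeding since the last contact, at any hospital. The SAE definition, with its planned-admission exclusion, then decides what counts.
3. At the first Version 00k visit, ask the same questions back to the last protocol visit. This also covers patients who left at 36 months and were re-contacted.
4. Reconcile the event follow-up rule across Severity and Causality Assessment and the two places in Documentation, Evaluation and Notification, so that only one rule applies.

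The cost is a wording amendment, a short visit prompt, a few minutes per visit and more unrelated events recorded. Because questioning would change during follow-up, the report should say from which visit the prompt applied, so that a later rise in recorded events is not taken for a rise in risk.

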## **IX. INVESTIGATIONAL DEVICE DISTRIBUTION AND ACCOUNTABILITY**

### **DEVICE ACCOUNTABILITY**

The Investigator is responsible for ensuring that the investigational devices are used only under the Investigator's supervision and are only used according to this protocol and any approved amendments. The Investigator will not supply an investigational device to any person not authorised to participate in the study. The Investigator shall maintain adequate records of the receipt and disposition of all investigational devices. The Investigator shall document in CRFs the lot numbers of the devices used during a case. In addition, the Investigator shall keep complete and accurate records of all devices used or unused in a Device Accountability Log, provided by the Sponsor, that have been returned to Harpoon Medical.

### **RETURN OF DEVICES**

All unused investigational devices will be returned to the study Sponsor upon completion of the clinical study. All used investigational devices will be properly disposed of, per institutional procedures. Any investigational device that fails to perform correctly will be immediately returned to the study Sponsor for analysis. The Investigator or his/her designated representative is responsible for device accountability and disposition of all used and unused devices. The study Sponsor or its designated representative will conduct device reconciliation at the completion of patient enrollment or at the conclusion of the study.

## X. STATISTICAL ANALYSIS

Based on the sample size calculations below, a total of 30 patients should be sufficient to demonstrate statistical non-inferiority of the Harpoon Medical device to other devices currently on the market in the EU for less-invasive mitral valve repair in the beating heart with a 90% power using a two-sided  $\alpha$  of 0.05 (one-sided 0.025). The clinical investigation of the Harpoon Medical device involves a multi-center study conducted across multiple countries and up to a total of 20 patients will be enrolled in the UK. Data collected from the first 30 patients enrolled across all sites will be used to support the CE mark of the Harpoon Medical device. Therefore, data from some or all of the 20 patients enrolled in the UK, depending on the timing of enrollment, will be used to support the CE mark of the Harpoon Medical device. The estimated enrollment period for the study is up to 24 months, and all patients shall be followed for 30 days, 6 months, 12 months, 18 months, 24 months, 30 months, 36 months, 48 months and 60 months after implantation in accordance with the Clinical Investigations schedule provided in Section VIII.

Currently, there are two (2) Class III reference devices on the market in the EU for treating MR due to one or more prolapsed leaflets (degenerative MR): the MitraClip device and the NeoChord DS1000. Both of these devices were designed to reduce MR on a beating heart without the need to arrest the heart or place the patient on cardiopulmonary bypass. The primary and secondary endpoints used to support CE mark for these devices were: freedom from death and MACE, freedom from surgery for mitral valve repair or replacement, and a reduction of MR to grade  $\leq 2$ . The studies performed in support of CE mark for both the NeoChord and MitraClip devices reported 30 day response rates.

For the MitraClip device, data following treatment with the MitraClip implant demonstrated a success rate for mitral regurgitation reduction to  $\leq$  grade 2 in 58% (14/24 patients) at 30 days, and 54% at 6 months (13/24 patients) (Feldman et al., 2005). In a subsequent randomised trial of MitraClip compared to surgical treatment of mitral valve regurgitation, the success rate was 55% at 12 months (100/181 patients) (Feldman, et al., 2011).

For the initial CE Mark Study of the NeoChord DS1000, data from 30 patients at seven (7) study centers at 30 days post-implant was evaluated in support of the CE Mark. In this study, the primary composite outcome was assessed in patients in whom at least one chordae tendineae was placed using the NeoChord DS1000 System. The composite endpoint consisted of the following elements:

- a reduction in mitral regurgitation  $\leq 2+$  at the time of the procedure AND
- MR reduction of  $\leq 2+$  at 30 days AND
- The rate of Major Adverse Events (MAE) defined as a combined endpoint of: death, MI, reoperation for failed surgical repair, non-elective cardiovascular surgery to treat an adverse event, procedural ventilation  $> 48$  hours, procedure-related transfusion of  $> 2$  units blood product, stroke, renal failure, deep wound infection, new onset of permanent AF, and septicemia, through 30 days.

Based on this definition, the response rate was 57% (17/30 patients) (Seeburger et al., 2014). In two subsequent single-center reports, the composite success rate using the NeoChord DS1000 was 85% (11/13 patients) at 6 months post-procedure (Rucinskas, et al., 2014) and 87% (54/62 patients) at 30 days post-procedure (Colli, et al., 2015). Combining these results, irrespective of the time of assessment of the primary endpoint, the average success rate among these studies is 68%, the standard deviation of the response rate is 15%, and the lower limit of one-sided 95% confidence intervals (CI) is approximately 50%.

An inferiority margin of 10% was selected as appropriate because it is a more stringent requirement than the lower bound of the 95% confidence interval of the average response rates in these previous studies. This non-inferiority delta reflects the diversity of the patients treated, the diversity of the causes of MR, the variety of non-beating heart methods available to treat MR, and the range of reported performance using similar techniques.

Using the historical control (HC) rate of 68% and a non-inferiority margin of 10%, the null and alternative hypotheses of the primary performance endpoint can be written as:

$$H_0: \pi_{\text{Harpoon\_performance}} \leq \pi_{\text{HC\_performance}}$$

$$H_A: \pi_{\text{Harpoon\_performance}} > \pi_{\text{HC\_performance}}$$

where,

$$\pi_{\text{HC\_performance}} = 68\% \text{ historical control rate} - 10\% \text{ Delta}$$

$$\pi_{\text{Harpoon\_performance}} = \text{Harpoon Medical system success rate}$$

The hypotheses for the primary performance endpoint can be rewritten as:

$$H_0: \pi_{\text{Harpoon\_performance}} \leq \text{HC \%}$$

$$H_A: \pi_{\text{Harpoon\_performance}} > 58\%$$

To achieve 90% power using a two-sided  $\alpha$  of 0.05 (one-sided 0.025), the sample size was estimated based on a single sample compared to a constant (0.58). Based on this calculation, 26 patients are required to demonstrate non-inferiority. To adjust for patients lost to follow-up, we have decided to enroll up to 30 patients in the TRACER Trial. Moreover, 30 patients has been a sufficient number of patients to provide a satisfactory profile of the adverse events likely to occur with beating heart mitral valve repairs in the aforementioned studies. Last, 30 patients is consistent with the sample size of previous beating heart, mitral valve repair devices. For example, the CE mark trial of the NeoChord DS1000 was conducted in 30 patients.

These data from these 30 patients shall be used to assess the safety and performance of the device when used on a human patient. All data shall be captured on an intent-to-treat basis. Data shall be reported as descriptive statistics.

The percentage of patients with improvements in MR reduction at the conclusion of the procedure, at the time of the hospital dismissal and at 30 days, six months, one, two, three, four and five years will be assessed. Specifically the percentage of patients that demonstrate MR reduction from “severe” to less than or equal to “moderate” at the conclusion of the procedure and at 30 days. While the number of subjects missing the primary endpoint of improvement in MR is anticipated to be small, if any, the following algorithm will be used to impute missing observations:

- Subjects who die prior to evaluation at 30 days or fail the procedure will be considered failures for the primary analysis.
- Patients lost after the procedure for other reasons will have their last observation carried forward (from procedure to 30 days). Should this situation occur, an additional sensitivity analysis, a tipping point analysis, will be conducted whereby each subject missing 30 day follow-up will be counted as a failure in succession, and the number of subjects with

missing data imputed as failures which “tip” the analysis to non-significance will be reported.

Freedom from Serious Adverse Events (SAEs) during the ePTFE implantation procedure, at discharge, and at 30 days follow-up will be tabulated. The number of patients experiencing one or more AEs or SAEs at 30-days post-procedure, the percentage of patients, and the exact 95% confidence limit will be calculated. Patients who die prior to 30 days will be considered failures for this analysis.

Freedom from Serious Adverse Events (SAEs) at 6 months, 12 months, 18 months, 24 months, 30 months and 36 months follow-up shall be tabulated. The number of patients experiencing one or more AEs or SAEs at 6 months, 12 months, 18 months, 24 months, 30 months, 36 months, 48 months and 60 months follow-up, the percentage of patients, and the exact 95% confidence limit will be calculated.

These data shall be used to assess the safety and performance of the Harpoon Medical device, and are not designed to test a statistical hypothesis, and therefore a formal sample size has not been calculated. All data shall be captured on an intent-to-treat basis. Data shall be reported as descriptive statistics.

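### The 58% benchmark rests on an average of unlike endpoints, so passing it means meeting a performance goal, not like-for-like non-inferiority to marketed devices; the net direction of bias is unknown

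*Combined protocol and SAP*

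**What the plan says.** Section X (Statistical Analysis) opens by saying that 30 patients are "sufficient to demonstrate statistical non-inferiority of the Harpoon Medical device to other devices currently on the market in the EU". It then describes the published results for two reference devices.

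- **MitraClip.** MR reduction to grade 2 or less was seen "in 58% (14/24 patients) at 30 days, and 54% at 6 months (13/24 patients"). For a later randomised trial "the success rate was 55% at 12 months (100/181 patients"), with no definition of success.
- **NeoChord, CE-mark study.** The composite required MR of 2+ or less at the procedure and again at 30 days, plus a third element: "The rate of Major Adverse Events (MAE) defined as a combined endpoint of: death, MI, reoperation for failed surgical repair", and further events through 30 days. It was assessed only in patients who had at least one chord placed. "Based on this definition, the response rate was 57% (17/30 patients").
- **NeoChord, two single-centre reports.** In one, "the composite success rate using the NeoChord DS1000 was 85% (11/13 patients) at 6 months post-procedure". The other gives 54/62 (87%) at 30 days. The elements of these composites are not restated.

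The plan then averages: "Combining these results, irrespective of the time of assessment of the primary endpoint, the average success rate among these studies is 68" (per cent), with an SD of 15% and a lower limit of about 50%. It subtracts a 10-point margin and sizes the study as one sample against the constant 0.58.

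TRACER's primary performance endpoint (Section IV, Performance Goals) is implantation of at least one chord with MR no worse than moderate at the end of the procedure and at 30 days. Section X counts death before 30 days and a failed procedure as failures and works on an intent-to-treat basis. Freedom from serious adverse events is tabulated separately.

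**The concern.** A non-inferiority claim needs the reference rate and the trial rate to measure the same thing. Here they do not. A TRACER patient with a non-fatal stroke, myocardial infarction or renal failure can still be a performance success. The same patient would fail the NeoChord CE-mark composite. Section X itself names "freedom from death and MACE, freedom from surgery for mitral valve repair or replacement" among the endpoints used for the reference devices, yet non-fatal events never enter the comparison with 58%. The reports also differ in assessment time (30 days to 12 months) and in denominator, and no adjustment for either is described.

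What is at stake is the wording of the conclusion. A result above 58% supports a statement about a fixed goal. It does not by itself show that the device is no worse than MitraClip or NeoChord, because the goal moves with the choice of reports treated as the reference.

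**Working it through.** **Inputs (all from Section X)**

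| Report | Success as described | Time | Count | Rate |
|---|---|---|---|---|
| MitraClip, first study | MR grade only | 30 days | 14/24 | 58.3% |
| MitraClip, first study | MR grade only | 6 months | 13/24 | 54.2% |
| MitraClip, randomised trial | not defined | 12 months | 100/181 | 55.2% |
| NeoChord, CE-mark study | MR at two times plus adverse events, chord placed | 30 days | 17/30 | 56.7% |
| NeoChord, single centre | composite, elements not restated | 6 months | 11/13 | 84.6% |
| NeoChord, single centre | composite, elements not restated | 30 days | 54/62 | 87.1% |

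**Step 1: reproduce 68%.** The three NeoChord rates alone average (56.7 + 84.6 + 87.1)/3 = 76.1%, so MitraClip rates must be in the average. All six rates average 66.0%. Two MitraClip rates with the three NeoChord rates give:

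| MitraClip rates used | Unweighted mean | Pooled by patient |
|---|---|---|
| 30 days and 12 months | 341.9/5 = 68.4% | 196/310 = 63.2% |
| 30 days and 6 months (same 24 patients twice) | 340.9/5 = 68.2% | 109/153 = 71.2% |
| 6 and 12 months | 337.8/5 = 67.6% | 195/310 = 62.9% |

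All three means round to 68%. The stated SD of 15% does not settle the choice. In population form the second set gives 14.5% and the third 15.0%, and their pooled rates lie on opposite sides of 68%. So the stated figure reproduces, but its make-up is not identified, and even the direction of the weighting effect is unknown.

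**Step 2: sensitivity of the goal.** Goal = reference rate minus 10 points. The plan names no test, so I assume an exact one-sided 0.025 binomial test with n = 30. The pass mark is the smallest k with P(X ≥ k | 30, goal) ≤ 0.025.

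| Reference (illustrative except the stated goal) | Goal | Pass mark | Tail |
|---|---|---|---|
| NeoChord CE-mark study, 17/30 | 46.7% | 20 | 0.0218 |
| MitraClip MR only at 30 days, 14/24 | 48.3% | 21 | 0.0136 |
| Pooled 196/310 | 53.2% | 22 | 0.0199 |
| 30-day reports, mean 67.4% | 57.4% | 23 | 0.0229 |
| **Stated goal** | **58.0%** | **24** | **0.0099** |
| Pooled 109/153 | 61.2% | 24 | 0.0238 |
| 30-day reports pooled, 85/116 = 73.3% | 63.3% | 25 | 0.0147 |
| NeoChord mean, 76.1% | 66.1% | 26 | 0.0105 |
| NeoChord pooled, 82/105 = 78.1% | 68.1% | 26 | 0.0182 |

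A normal-approximation test also gives marks from 20 to 26, with 23 at 58%. By either method, 22/30 passes the 53.2% goal but not 58%, and 24/30 passes 58% but neither NeoChord-only goal.

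**Step 3: precision of the one rate shown to include adverse events.** The exact (Clopper-Pearson) 95% interval for 17/30 is 37.4% to 74.5%.

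**Step 4: direction of the mismatches.** Adverse events inside a historical composite lower that rate and make the goal easier for TRACER. Later assessment may do the same where success fades (14/24 to 13/24 in the one study reported twice). Counting only patients with a chord placed raises the historical rate and makes the goal harder. Set beside MR-only rates, TRACER's two-time-point requirement and its death rule also make it harder. The denominator gap may be small, because Section VII (Enrollment) confirms enrolment only after intra-operative assessment of valve suitability. The documents give no count of patients who failed only through an adverse event, so these effects cannot be netted.

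**The case against.** The plan is open about much of this. It calls 68% a historical control rate and says the comparison is with a constant. It gives the SD and the lower limit, argues that the resulting goal is stricter than that limit, and explains the margin by the diversity of patients, causes and methods. It says that data are reported descriptively, and Section X closes by saying that the data are not designed to test a hypothesis. Safety is tabulated in its own right. The single centres' rates are called composite straight after the CE-mark definition, so they may use the same elements. The subsets above are also mine: the plan names two reference devices and justified its margin against the whole set.

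Much of that stands. The subsets show sensitivity only and are not the plan's comparator. But a spread of rates and a diversity rationale do not align endpoint, time point or denominator. The descriptive wording sits in the same section as the explicit non-inferiority claim and does not withdraw it.

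A reader might infer that leaving out adverse events makes 58% a lenient goal that favours the device. The documents do not support this, because other mismatches run the other way and none can be sized. Nor can one say that unweighted averaging made the goal harder: that holds for two of the three sets in Step 1 and reverses for the other.

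**Conclusion.** The concern holds in a limited form. No stated rate is shown to be wrong, and 68% reproduces. What goes too far is the claim of non-inferiority to marketed devices. The design can support a statement that the success rate did or did not exceed a fixed goal of 58%.

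The size is given by the pass mark: 24 of 30 at the stated goal, and 20 to 26 over illustrative reference sets. This rests on the 10-point margin being held, 30 analysed patients, and an assumed exact one-sided 0.025 test. The net direction of bias and the effect of adverse events are not established. Enrolment is complete (Section II) and the CE mark has been granted (Section III, Potential Risks), so the consequence is for how the result is reported.

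**What to change.** **Wording.** In Section X and in the report, state the conclusion as meeting or not meeting a 58% performance goal, in place of non-inferiority to marketed devices.

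**Disclosure.** State which reports and what weighting give 68%, list each source's endpoint, time point and denominator, and show the alternative averages.

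**Optional supportive table**, labelled as added after enrolment closed and not tested against 58%:

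- Report the proportion with MR no worse than moderate at the procedure and at 30 days and free of the listed major adverse events through 30 days, with an exact 95% interval, by intent-to-treat and in patients with a chord placed.
- Use adjudicated events where available and site-reported events otherwise, as Section XI (Clinical Endpoint Committee) already provides.
- Place it beside 17/30 (37.4% to 74.5%), and beside 11/13 and 54/62 with a note that their elements are not restated.
- Disclose that the documents give no mapping between a 2+ grade and moderate MR. Disclose also that renal failure, permanent atrial fibrillation, prolonged ventilation and transfusion would come from adverse event records or source notes, not from scheduled tests, so the composite may be overstated.

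**Cost.** No new visits. Some derivation work, an ethics committee submission if Section X is reworded, and a narrower conclusion. The composite rate cannot exceed the MR-based rate in the same patients.
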